 - i. Greater than 2 patients who have any grade 4 or higher toxicity during radiation. If a patient has a grade 4 or higher toxicity, then they will be taken off the study, administered a lower dose per fraction per the treating physician, and the study will be closed. We do expect grade 3 skin toxicity (moist desquamation in areas other than skin folds), as many patients have tumors that extend to the surface of the skin and thus will need to be bloused to get the appropriate dose to these areas. Thus, moist desquamation often occurs.
 - ii. ≥60% of patients with post-operative wound complications.
 - iii. As mentioned above, patients may also withdraw at any point if they wish to not be on study.
- C. The research coordinator and PI will be notified of the withdrawal of a patient and the appropriate documentation will be made.
 - i. The IRB will be notified at the time of withdrawal.
- D. Subjects will not be replaced.
- E. Follow up and data collection for withdrawn subjects will terminate at the time of withdrawal.
- F. Dose Modification
 - i. If any grade 4 toxicity occurs, the dose will be modified based on the BED calculator above and the study will be closed.

XI. **Endpoint Assessment**

- A. Study Design:
 - i. This is a non-randomized Phase II pilot protocol to determine the feasibility, toxicity, and disease control (local control, overall and progression-free survival) using hypofractionated pre-operative radiation therapy in patients with primary localized STS.
- B. Primary Endpoint:

- i. The primary aim of this study is to assess local control. We expect local recurrence rates of <7%. Local and regional recurrence will be defined for each lesion per the treating physician(s). Local recurrence will be defined if the patient has evidence of disease on imaging (MRI or CT or PET CT) or physical exam.

C. Secondary Endpoint:

- i. The secondary objective of this study is to assess quality of life, toxicity (see iii), disease-free survival and overall survival. Disease-free survival is defined as the time from enrollment until documented disease-recurrence or death, whichever occurs first. Patients who are disease-free and alive at the time of analysis will be censored at the time of their last follow-up. Patients will be followed for disease-free survival for a minimum of 2 years.
- ii. Quality of life will be assessed via the FACT-L forms and given at the specified time points above.

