- A. The primary aim of a 2-year local recurrence rate of less than 3% will be evaluated by a one-sided equivalence test with an equivalence limit of 5% and a type I error rate of 10%. The study will conclude equivalence if the 2-year cumulative incidence of recurrence is less than 12% at the 0.10 type I error level. Power calculations are based on exact binomial probability calculations with an equivalence determined by no more than 12% local recurrence rate (within 5% of 7%), assuming a true 2-year local recurrence rate of 2.5%.
- B. If the true local recurrence rate is 12%, then with 35 patients the probability of observing a recurrence rate of 3.1% or less (≤ 1 of 35) is 8.97% (one-sided type I error = 0.0897).
- C. If the true local recurrence rate is 2.5%, then with 35 patients the probability of observing recurrence of 3.1% or less (≤ 1 out of 35) is 81.0% (Power).
- D. This is as close as we can get to a one-sided equivalence test with 10% type I error and 80% power with exact binomial calculations. The probability of falsely rejecting the null hypothesis (*hypofractionation treatment is worse than standard*) with only 0 or 1 recurrence out of 35 patients is less than 10% if the actual recurrence rate is 12% or more. There will be at least 80% power to reject this hypothesis if the true recurrence is 2.5% or less.

XIV. Considerations for Toxicity, QOL, Disease-Free Survival and Overall Survival (Secondary Endpoints)

- A. Overall survival and disease-free survival will be estimated using the product limit estimator and presented as Kaplan-Meier plots. Cumulative incidence rates will be calculated for local recurrence and adverse events. Quality of life data will be summarized for each time point, and compared using non-parametric statistical methods.
- B. Toxicity will be measured via the CTCAE v. 4.0 and the MSTS score. We will compare toxicity to the standard historical control for preoperative radiation therapy in STS (NCIC, O'Sullivan et. al) (5)
- C. Quality of Life will be measured with the FACT-L validated questionnaire.

XV. References

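### The stated primary aim (2-year local recurrence below 3%) is not the hypothesis tested (below 12%), and the printed cut-off, type I error and power belong to 32 patients, not 35

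*Combined protocol and SAP*

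**What the plan says.** Section XIII.A sets the aim: "The primary aim of a 2-year local recurrence rate of less than 3% will be evaluated by a one-sided equivalence test". The margin is 5 points and the one-sided level is 0.10. The section then gives the decision criterion: "The study will conclude equivalence if the 2-year cumulative incidence of recurrence is less than 12% at the 0.10 type I error level". The 12% is explained as "equivalence determined by no more than 12% local recurrence rate (within 5% of 7"%, that is, 7% plus 5 points. Power is calculated "assuming a true 2-year local recurrence rate of 2.5"%.

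Section XI.B, on the primary endpoint, gives a different figure again: "We expect local recurrence rates of <7"%.

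Section XIII.B takes a sample of 35 and a true rate of 12%, and states: "the probability of observing a recurrence rate of 3.1% or less (≤ 1 of 35) is 8.97"%. Section XIII.C gives 81.0% as the power of the same rule at a true rate of 2.5%. Section XIII.D says that the error is below 10% if the true rate is 12% or more, and that power is at least 80% if it is 2.5% or less. Section X.A sets the sample size at 35, and X.D says that patients who leave are not replaced.

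**The concern.** Four percentages describe one endpoint. Three have a clear role: 7% is the reference, 12% is the null boundary and 2.5% is the rate assumed for power. The fourth, 3%, is called the primary aim, yet nothing in the test uses it.

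This is the only primary endpoint of a single-arm study, so the hypothesis as written fixes what the trial may conclude. If the aim sentence stands, a pass could be read as evidence that recurrence is below 3%, which the design cannot provide.

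The printed cut-off of 3.1% is a second warning sign, because 1 divided by 35 is not 3.1%. If the cut-off was worked out for another sample size, the type I error and power beside it may have been too.

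**Working it through.** **Inputs.** Null boundary 12%, power assumption 2.5%, one-sided level 0.10 and aim <3% (XIII.A); rule ≤1 recurrence and n = 35 (XIII.B to XIII.D). The calculation treats all 35 patients as having known 2-year status, as the plan's binomial calculation does.

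**Formula.** For X recurrences in n patients with true rate p:

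P(X ≤ 1) = (1 − p)^n + n·p·(1 − p)^(n−1)

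**Step 1: the plan's own figures, at n = 35.**
- At p = 0.12: 0.88^35 + 35 × 0.12 × 0.88^34 = 0.0114 + 4.2 × 0.01295 = 0.0658. The plan prints 0.0897.
- At p = 0.025: 0.975^35 + 35 × 0.025 × 0.975^34 = 0.4123 + 0.875 × 0.4228 = 0.782. The plan prints 0.810.
- Cut-off: 1/35 = 2.9%. The plan prints 3.1%.

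None of the three is reproduced.

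**Step 2: which n gives the printed figures?** The rule ≤1 of n, for n near 35:

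| n | 1/n | Type I error at 12% | Power at 2.5% |
|---|---|---|---|
| 32 | 3.1% | 0.0897 | 0.810 |
| 33 | 3.0% | 0.0810 | 0.801 |
| 34 | 2.9% | 0.0730 | 0.791 |
| 35 | 2.9% | 0.0658 | 0.782 |

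All three printed figures match n = 32. Power is already below 80% at n = 34.

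**Step 3: what a pass shows.** The exact one-sided 90% upper limit is the p at which the probability of seeing that many recurrences or fewer equals 0.10.
- 0 of 35: 1 − 0.10^(1/35) = 6.4%.
- 1 of 35: solving (1 − p)^35 + 35·p·(1 − p)^34 = 0.10 gives p = 10.7%.
- 2 of 35 (a fail): 14.5%.

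Both passing results exclude 12%, and neither excludes 3%.

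**Step 4: could any result support <3%?** The most favourable result is 0 of 35. Its exact p-value against a true rate of 3% is 0.97^35 = 0.344, far above 0.10. With no recurrences at all, excluding 3% needs ln(0.10)/ln(0.97) = 75.6, so 76 patients.

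**Step 5: how often the rule passes at other true rates, n = 35.** It passes with probability 71.7% at a true 3% and 28.7% at a true 7%. A pass is thus compatible with recurrence at the reference rate itself.

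**The case against.** The strongest defence is that the operative test can be identified despite the aim sentence. XIII.A says what the 5 points are added to, XIII.B and XIII.D tie the type I error to 12%, and the rule of 0 or 1 in 35 is explicit. An analyst following XIII.B to XIII.D would run the same test with or without the 3%. This stands, and it is why the rule need not change. It does not rescue the aim sentence, which still names a claim that the test does not address.

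A second defence is that <3% was meant as an observed cut-off: 1/35 is 2.9% and passes, while 2/35 is 5.7% and fails. That is plausible, but the text calls it the aim that the test evaluates. If an observed cut-off was meant, the plan should say so.

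Third, an expectation below 7% and an assumed 2.5% for power do not contradict each other, and XIII.A already labels 2.5% as an assumption. That is correct. XI.B needs aligning only so that the role of 7% as reference is plain.

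A reader might also go further and add the 5-point limit to the 3% aim, giving a limit of 8%, at which the rule would pass 21.8% of the time, more than twice the stated error. The documents do not support this. They never print 8%, and the same paragraph attaches the 5 points to 7%. That anchor agrees with XI.B and with the 93% local control that the Introduction reports for conventional pre-operative radiation. Against the written null of 12% the error is 6.6%, within the 10% allowed.

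**Conclusion.** The point holds. The declared aim of <3% is not the hypothesis tested, and with 35 patients no result can show a true rate below 3% at one-sided 0.10. The best attainable upper limit is 6.4%, and a pass supports only a rate below 12%.

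The printed cut-off, type I error and power are wrong for 35 patients: 2.9%, 6.6% and 78.2%, in place of 3.1%, 8.97% and 81.0%. The error moves in the safe direction. Power falls 2.8 points below the printed value and 1.8 points below the 80% promised in XIII.D, which is a small shortfall but makes that sentence untrue.

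Two further inferences should be resisted. Type I error is not inflated. Nor do the documents say that a pass will be reported as showing <3%; the wording merely leaves room for it.

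The figures assume that 2-year status is known for all 35 patients. It is possible that 32 evaluable patients out of 35 were intended (a loss of 3/35 = 8.6%), but the documents mention neither 32 nor any allowance for loss.

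**What to change.** - **XIII.A:** state H0 as 2-year local recurrence ≥12% (7% reference plus 5 points) and H1 as <12%, rejecting H0 if at most 1 of 35 patients recurs (2.9%). Delete <3% as the aim, or label it explicitly as the observed-rate cut-off. Keep 2.5% as the rate assumed for power only.
- **XI.B:** align with this by naming 7% as the reference rate and 12% as the limit tested.
- **XIII.B to XIII.D:** replace the printed figures with a 2.9% cut-off, 6.6% type I error and 78.2% power, and withdraw the statement of at least 80% power. If 32 evaluable patients were intended, say so, give the allowance for loss, and write the rule and figures for 32.
- **Reporting:** give the exact one-sided 90% upper limit with the result, and state that a pass supports a rate below 12%.

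The cost is protocol wording. If 35 is kept, the decision rule and sample size do not change. The stated claim and power become slightly less favourable.

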Pilot Study Evaluating Hypofractionated Preoperative Radiation Therapy for Soft Tissue Sarcomas of the Extremity and Chest-wall

I. SCHEMA

	Preoperative Image Guided Radiation Therapy (3D CRT or IMRT)	Surgery
Register	All patients:	All patients
	Patients with stage I to III STS of the extremity or chest wall who receive neoadjuvant, adjuvant, or no chemotherapy	Limb sparing surgery 4 to 8 weeks after completion of radiation therapy
	Radiation Dose: 35 Gy in 5 fractions (7 Gy per fraction)	

Patient Population:

Patients with localized, stage I-III histologically confirmed soft tissue sarcomas of the extremity and chest-wall primaries will be eligible for this study. Patients must be medically operable and have not had prior radiation therapy to the primary sarcoma site.

II. INTRODUCTION

There has been an evolution in management for patients with soft tissue sarcomas (STS) of the extremity since the 1970's. Historically, amputation was the mainstay of treatment. However, multimodality therapy with limb-sparing surgery and radiation with or without chemotherapy has been shown to yield equivalent control and survival for patients who underwent non-limb salvage techniques (1, 2). Thus, more conservative therapies have been employed.

The sequence of radiation therapy (RT) has also been examined in the treatment of STS of the extremity. Post-operative radiation is typically administered within 4 to 6 weeks after limb-salvage surgery; however, this may be technically challenging due to the lack of a known mass, large radiation fields, and higher radiation doses in the post-operative setting. The advantages of pre-operative radiation include, but are not limited to, lower radiation dose and field size, facilitation of surgical resection, improved tumor oxygenation and less long term toxicity. Thus, the use of pre-operative radiation therapy has been investigated and been shown to be feasible, and it can lead to excellent rates of local control and survival.

DeLaney, et al. examined the use of neoadjuvant interdigitated chemotherapy and radiation in 48 patients with ≥ 8 cm STS of the extremity. Patients received mesna, Adriamycin, Ifosfamide and Dacarbazine (MAID) followed by radiation therapy to 22 Gy at 2 Gy per fraction. This sequence was repeated once followed by limb-salvage surgery and 3 additional cycles of MAID. In this study, 5-year local control was 92% and 5-year disease-free and

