overall survival were 75% and 44%, respectively. Both disease-free and overall survival was significantly improved compared to historical controls (3). This study led to the development of a national study that used a similar interdigitated method of treatment (4).

RTOG 95-14 was a phase II study that enrolled 64 patients with large (≥ 8 cm) grade 2 to 3 STS of the extremity or torso. Patients received a similar sandwich course of therapy, which included chemotherapy with MAID followed by radiation therapy to 22 Gy at 2 Gy per fraction. As in the Delaney *et al.* protocol, this sequence was repeated once followed by limb-salvage surgery and 3 additional cycles of MAID. The 3-year local-regional recurrence rate was 10% (when amputation was not considered a failure). The 3-year disease free and distant-disease free and overall survival was 57%, 64%, and 75%, respectively. However, toxicity was the limiting factor in this study, with 5% treatment-related deaths (mostly secondary AML) and an 84% rate of grade 4 toxicity. Thus the toxicity precluded further use of this regimen in future studies (4). One caveat of this study was that higher chemotherapy doses were used and thus thought to contribute to the added morbidity in patients enrolled on this study.

Although there are several advantages to pre-operative radiation therapy, it had remained unclear if pre-operative radiation led to poorer control or survival to the counterpart patients who received post-operative radiation until completion of the NCI Canadian Trial.

O'Sullivan, *et al.* randomized 190 patients (out of 266 planned) with localized STS of the limb to pre-operative RT to 50 Gy in 25 fractions versus post-operative RT to 66 to 70 Gy. Patients with positive margins in the pre-operative RT arm received a 16 to 20 Gy boost. At 5 years, the local control between the pre-operative and post-operative RT cohorts was 93% and 92%, respectively. There was no difference in relapse-free (58% versus 59%, $p=NS$) and overall survival (73% versus 67%, $p=NS$). The authors concluded that pre- and post-operative RT were equally effective in terms of disease control and survival (5).

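### The 12% limit at 2 years rests on a 7% standard rate with no stated source or time point, and the only matching figure in the documents is a 5-year result

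*Combined protocol and SAP*

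**What the plan says.** All references are to the combined protocol and SAP.

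- **XIII.A, test.** The primary test is a "one-sided equivalence test with an equivalence limit of 5% and a type I error rate of 10" percent. The decision is: "The study will conclude equivalence if the 2-year cumulative incidence of recurrence is less than 12% at the 0.10 type I error level".
- **XIII.A, limit.** The calculations rest on "no more than 12% local recurrence rate (within 5% of 7%), assuming a true 2-year local recurrence rate of 2.5" percent. The limit is therefore 7% + 5 points = 12%, applied at 2 years.
- **XIII.B to D.** The rule is at most 1 recurrence in 35 patients, with a stated type I error of 8.97% and power of 81.0%. XIII.D words the null hypothesis as the hypofractionated regimen being inferior to standard treatment.
- **XI.B.** The only other mention of this figure is "We expect local recurrence rates of <7" percent, again with no source and no time point.
- **II, Introduction.** For the randomised trial of 50 Gy in 25 fractions before surgery against post-operative radiation: "At 5 years, the local control between the pre-operative and post-operative RT cohorts was 93% and 92%, respectively".
- **XI.D.** Results are to be compared with a retrospective institutional database of patients given conventional pre-operative radiation in 2000-2012, using crude rates. No rate from that database is given.

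**The concern.** A margin of 5 points over standard has meaning only if the standard rate and the trial rate refer to the same follow-up time. Cumulative incidence cannot fall as follow-up lengthens. If 7% is a 5-year rate, adding 5 points to it and applying the sum at 2 years sets the trial's early rate against a later one.

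What is at stake is the claim the trial can make. III.A hypothesises local control similar to conventional fractionation, and XIII.A calls a pass equivalence. If the reference is not a 2-year rate, a pass shows that the 2-year rate is below 12%. It does not show that the rate is within 5 points of standard at 2 years.

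**Working it through.** **1. The plan's own figures.** For at most 1 event in n patients, P = (1−p)^n + n·p·(1−p)^(n−1).

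- n = 35, p = 0.12: 0.0114 + 0.0544 = 6.6%. At p = 0.025: 78.2%.
- n = 32, p = 0.12: 8.97%. At p = 0.025: 81.0%. Also 1/32 = 3.1%.

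The stated 8.97%, 81.0% and 3.1% belong to 32 patients, not 35. That is a separate matter. The rest of this check uses 35, as the plan states.

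**2. Where 7% could come from.** The timed recurrence figures for pre-operative radiation without hypofractionation, all in the Introduction, are:

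- Randomised trial, 50 Gy in 25 fractions: 100 − 93 = 7% at 5 years.
- Interdigitated chemotherapy and radiation series: 100 − 92 = 8% at 5 years.
- Phase II chemotherapy and radiation trial: 10% local-regional recurrence at 3 years.

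None is a 2-year rate. Only the first gives 7%, and it is also the only one using the standard schedule.

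**3. Direction.** If 7% is the 5-year rate and a share f < 1 of those recurrences occurs by year 2, the standard 2-year rate is 7% × f, which is below 7%. Then 12% − 7% × f is more than 5 points. This step needs no outside data.

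**4. Size.** The documents do not give the timing of recurrence, so f is an assumption. The constant-hazard case gives 1 − 0.93^(2/5) = 2.86%, that is f = 2.86/7, about 41%. The time-matched limit is the standard 2-year rate + 5 points. The last column is the probability of at most 1 in 35 at that limit. Death as a competing event is ignored.

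| Share by year 2 | Standard at 2 years | Matched limit | 12% minus standard | P(at most 1 of 35) at matched limit |
|---|---|---|---|---|
| Constant hazard | 2.86% | 7.86% | 9.1 points | 22.7% |
| 60% | 4.2% | 9.2% | 7.8 | 15.5% |
| 70% | 4.9% | 9.9% | 7.1 | 12.6% |
| 80% | 5.6% | 10.6% | 6.4 | 10.2% |
| 85% | 5.95% | 10.95% | 6.0 | 9.2% |
| 90% | 6.3% | 11.3% | 5.7 | 8.2% |
| 100% | 7.0% | 12.0% | 5.0 | 6.6% |

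Example at 60%: 0.908^35 + 35 × 0.092 × 0.908^34 = 0.034 + 0.121 = 15.5%.

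**5. Where the error crosses 10%.** P(at most 1 of 35) = 10% at p = 10.66%. Then f = (10.66 − 5)/7 = 81%. With 81% or more of recurrences by year 2, the rule keeps the error for a true 5-point excess at or below 10%. With less, it does not.

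**The case against.** The strongest objection is to the premise. No sentence ties the 7% to the randomised trial. XIII.A uses it in a passage about 2-year rates, and the comparator named in XI.D for disease outcomes is the institutional database. Its rate is not shown, and 7% could be its 2-year figure. XIV.B names the randomised trial as historical control for toxicity only. Nor is 7% at 2 years implausible: the 3-year rate of 10% in the phase II trial is 1 − 0.90^(2/3) = 6.8% at 2 years under constant hazard, although that is a different regimen, in large grade 2 to 3 tumours, with a local-regional endpoint. All of this stands. The 5-year origin is an inference. XIII.A's assumed 2-year rate of 2.5% is close to the 2.86% that 7% at 5 years implies under constant hazard, but that is suggestive only.

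A reader might also infer that the trial would accept a regimen well over 5 points worse, or that the test is too lenient. The documents do not support that without conditions. The 12% is the null limit, not the pass mark. A regimen truly at 12% passes only 6.6% of the time, and 1 of 35 has a one-sided 90% exact upper bound of 10.7%. Excess error depends on an unknown timing of recurrence, and the 60% to 85% range is itself an assumption.

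Nor can it be said that follow-up stops at 2 years. Scheduled visits cover years 1 and 2 (VII), but XI.C sets 2 years as a minimum for disease-free survival.

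What remains is that the source and time point of the reference rate are unstated, that the only matching figure is at 5 years, and that no 2-year standard rate appears. An origin in the database would still leave the decision limit without a stated basis. The planned comparison in XI.D does not settle it, because crude rates do not align follow-up at 2 years.

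**Conclusion.** The point holds in conditional form. The documents do not establish that 12% at 2 years is 5 points above standard, so a pass does not support a conclusion of equivalence.

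If 7% is the 5-year rate, the limit is more than 5 points above standard at 2 years whenever any recurrence falls after year 2. The gap is 7.8 to 6.0 points if 60% to 85% of recurrences occur by then, and 9.1 under constant hazard. The error for a true 5-point excess is correspondingly 15.5% to 9.2%, or 22.7%. Whether it breaches 10% turns on the 81% threshold, which the documents cannot resolve. They do not show that the 7% is wrong, nor that the error rate is in fact inflated.

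**What to change.** - **XIII.A and XIII.D:** replace the conclusion of equivalence with the conclusion that the 2-year local recurrence rate is below 12%. State the source and time point of the 7%. Do not write that it is a 5-year figure unless the sponsor confirms this.
- **XI.D:** replace the crude-rate comparison for local recurrence with 2-year cumulative incidence in both the trial and the 2000-2012 database. Fix the database figure before the trial data are analysed.

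The cost is a wording amendment, one estimate from a database the sponsor already holds, and a slightly weaker claim. No more patients are needed. Some chart abstraction may be required: XI.D lists local recurrence and the date of last follow-up among the database variables but does not itemise dates of recurrence, so the sponsor should check that these are available.

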Hypofractionation has also been used in STS study and has been shown to have favorable outcomes (11). Kosela-Paterczyk, *et al.* prospectively studied 272 patients with stage I-III STS of the extremity or trunk wall to 5 Gy x 5 fractions (25 Gy total) daily. 3-year overall survival was 72% and local control was 80%. Factors that impacted survival were STS > 10 cm and grade 3 disease. Forty-two percent of patients had some form of toxicity in this study, with the majority being the expected acute erythema and desquamation observed with RT. Seven percent of patients needed surgery to address these toxicities, which included procedures for wound healing (debridement) and wound closure. Late toxicities occurred in 15% of patients and were mainly associated with limb edema and fibrosis. Another prospective study, Kubciek, *et al.*, assessed 12 STS of the extremity that were treated to 35 Gy in 5 fractions using stereotactic body radiation techniques. Median tumor size was 7.6 cm. In this study, the local control rate was 100% and the distant metastasis rate was 42%. Most patients had some form of erythema, dry or moist desquamation which resolved within 4 weeks after the completion of radiation. There were no wound complications or late toxicity (12).

Although there are studies demonstrating the feasibility of hypofractionated radiation therapy in STS, these studies do not correlate clinical outcomes with pathologic or radiologic changes seen after radiation has completed. Association of radiologic and pathologic impact from the treatment for STS is integral as it correlates to disease control in this setting. Thus, investigating these alterations on imaging and final pathology will provide a more complete understanding of the effects of hypofractionated radiation therapy in STS.

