Supporting Cytokine Analysis	Rutkowski, et al. 2002 (24)	Cytokine serum levels in soft tissue sarcoma patients: correlations with clinco-pathologic features and prognosis	Serum levels of some proinflammatory, hematopoietic and angiogenic cytokines and cytokine receptors are elevated, frequently in parallel, in a large percentage of soft tissue sarcoma patients. Significant correlations of serum cytokine levels with tumor size and grade suggest that some of these cytokines may be directly or indirectly involved in the progression of soft tissue sarcomas. Serum assays of IL-6, IL-8 and TNF RII before or after the treatment may be useful in establishing soft tissue sarcoma patients prognosis.

III. OBJECTIVES

- A. Hypothesis: We hypothesize that pre-operative hypofractionated radiation therapy for localized STS will result in local control and toxicity similar to conventional fractionation with less cost, more patient convenience and decreased overall treatment time.
- B. Objectives:
 - i. The primary objective of the study is to assess the local control, which will be assessed via physical exam and MRI.
 - ii. The secondary objectives are as follows:
 - 1. Assess toxicity, QOL using FACT-L
 - 2. Assess disease-free and overall survival using the product limit estimator and presented as Kaplan-Meier plots.
 - 3. Assess the acute and long term toxicity of hypofractionated pre-operative radiation for localized, stage I-III STS will be assessed via the CTCAE version 4.0 (Appendix III) and the Musculoskeletal Tumor Rating Scale (Appendix III).
 - 4. Assess radiologic changes due to hypofractionated radiation through the standard and advanced sequences of MRI
 - 5. Assess pathologic changes due to hypofractionated radiation through the expression of tumor biomarkers, percent necrosis, fibrosis and viable cells.

IV. ELIGIBILITY CRITERIA

- A. Inclusion Criteria
 - i. ≥ 18 years of age
 - ii. Biopsy obtained within 16 weeks prior to registration
 - iii. Pathologic confirmation of primary soft tissue sarcoma of the upper or lower extremity or chest wall. As per protocol per the STS tumor group, if biopsy was done at an outside hospital, then it will be reviewed by the pathologists at Froedtert and the Medical College of Wisconsin.
 - iv. Stage I-III Soft Tissue Sarcoma of the extremity or chest wall without evidence of metastatic disease (Appendix II)
 - v. Medically operable
 - vi. (History and Physical within 16 weeks of registration

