4. Place cryovials into biohazard bag and immediately freeze at -70 to -90°C.
5. Store frozen plasma until ready for testing.

IX. **Assessment of Safety, Dose Modifications and Dose Delays**

- A. This study will be reviewed by the Medical College of Wisconsin Cancer Center Data Safety Monitoring Committee (MCW CC DSMC). A summary of the MCW CC DSMC activities are as follows:
 - i. Review the clinical trial for data integrity and safety.

- ii. Review all unexpected grade 3, and all grade 4, and 5 adverse events, as well as any others requiring expedited reporting as defined in this protocol. (Grades 4 & 5 events must be reported to the DSMC within 5 calendar days of study staff's knowledge.) Review all DSM reports.
- iii. Sequential boundaries will be used to monitor the post-operative wound-complication rate. The accrual will be halted if excessive numbers of grade 3 or 4 (page 32) complications are seen, that is, if the number of complications is equal to or exceeds X out of N patients (X/N) with full follow-up (see below). This is a Pocock-type stopping boundary (Ivanova, et al. 2013) that yields the probability of crossing the boundary at most 5% when the complications rate is equal to 50% (O'Sullivan, et al. 2002).
- iv. Accrual will halt for protocol review if 6/6 (6 patients out of the first 6), then 7/7, 8/8, 9/10, 10/11, 11/13, 12/14, 13/16, 14/18, 15/19, 16/21, 17/22, 18/24, 19/26, 20/27, 21/29, 22/31, 23/32, 24/34, and 25/35 grade 3-4 treatment related AE's.
- v. Submit a summary of any recommendations related to study conduct.
- vi. Terminate the study if deemed unsafe for patients.
- B. A copy of the MCW Cancer Center Data and Safety Monitoring Plan and membership roster will be maintained in the study research file and updated as membership changes.
- C. The committee will review reports from the study PI twice annually (or more frequently if needed) and provide recommendations on trial continuation, suspension or termination as necessary.

X. **Subject Withdrawal Criteria**

- A. This Protocol is designed for 35 patients. Accrual will terminate early based on toxicity analysis. Patients may also withdraw at any point if they wish to not be on study.
- B. Criteria for early Closure

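### Section XIII gives power only at an unexplained 2.5% recurrence rate; with 35 patients that power is 78.2%, not 81.0%, and it falls to between 73.5% and 28.7% if the regimen merely equals the 7% standard

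*Combined protocol and SAP*

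**What the plan says.** Section III.A hypothesises that the short course "will result in local control and toxicity similar to conventional fractionation". Section XI.B adds: "We expect local recurrence rates of <7"%. Section XIII.A opens with an aim of a 2-year recurrence rate under 3% and then sets up a "one-sided equivalence test with an equivalence limit of 5% and a type I error rate of 10"%. The limit and the rate used for power appear together there: "no more than 12% local recurrence rate (within 5% of 7%), assuming a true 2-year local recurrence rate of 2.5"%.

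Section X.A states "This Protocol is designed for 35 patients". Sections XIII.B to D give the rule (0 or 1 recurrence in 35 rejects the hypothesis that the regimen is worse than standard), a type I error of 8.97% at a true 12%, and power of 81.0% at a true 2.5%. Section XIII.D concludes: "There will be at least 80% power to reject this hypothesis if the true recurrence is 2.5% or less". No power is given at any other rate. No reading is given for 2 or more recurrences beyond the null not being rejected.

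**The concern.** A claim of similarity is normally accompanied by its chance of success when the new treatment equals the standard. Here 7% anchors the limit, but the only power figure is at 2.5%, roughly a third of that anchor (2.5/7 = 0.36). The documents do not say where 2.5% comes from, or how an aim below 3%, an expectation below 7% and a limit of 7% plus 5% fit together.

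Two things are at stake. A reader takes from Section XIII that a regimen as good as the standard has about an 80% chance of passing. And the plan attaches no interpretation to the counts that would be most likely if the true 2-year rate were 7%.

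**Working it through.** **Inputs.** n = 35 (Section X.A; XIII.B and C); rule X ≤ 1; limit 12%; anchor 7%; assumed true rate 2.5% (Section XIII). For the standard, the Introduction gives 93% local control at 5 years with conventional pre-operative radiotherapy. All 35 patients are taken as evaluable at 2 years.

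**Formula.** P(pass) = P(X ≤ 1) = (1 − p)^n + n·p·(1 − p)^(n−1).

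**Step 1: the plan's own figures.**

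| n | Type I error, p = 12% | Power, p = 2.5% | 1/n |
|---|---|---|---|
| Stated for 35 | 8.97% | 81.0% | 3.1% |
| Computed, 35 | 0.0114 + 0.0544 = 6.58% | 0.4123 + 0.3700 = 78.2% | 2.86% |
| Computed, 32 | 0.0167 + 0.0730 = 8.97% | 0.4448 + 0.3649 = 81.0% | 3.125% |

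The three stated figures do not reproduce at 35, and all three reproduce at 32. With 35 patients, solving P(X ≤ 1) = 0.80 gives p = 2.36%, so 80% power is not reached at 2.5%.

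**Step 2: power at other true rates, n = 35.**

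| True 2-year rate | P(conclude equivalence) | P(miss the rule) |
|---|---|---|
| 2.5% | 78.2% | 21.8% |
| 3% | 71.7% | 28.3% |
| 5% | 47.2% | 52.8% |
| 7% | 0.0789 + 0.2078 = 28.7% | 71.3% |

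**Step 3: time scale.** The only figure in the documents that matches the 7% is a 5-year one (100% − 93%), while the test is at 2 years. No 2-year rate for the standard is given. Under an assumed constant hazard, the 2-year rate is 1 − 0.93^(2/5) = 2.86%, and P(X ≤ 1) = 73.5%. A regimen equal to the standard therefore misses the rule with probability between 26.5% (true rate 2.86%) and 71.3% (true rate 7%).

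**Step 4: what counts above 1 would show.** At a true 7%, P(2 to 4) = 0.2659 + 0.2201 + 0.1325 = 61.9% and P(5 or more) = 9.5%. One-sided 90% exact (Clopper–Pearson) limits:

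| Recurrences of 35 | Lower | Upper |
|---|---|---|
| 1 | – | 10.7% |
| 2 | 1.5% | 14.5% |
| 4 | 5.1% | 21.6% |
| 5 | 7.1% | – |

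From 2 to 4 recurrences the limits include both 7% and 12%. At 5 the lower limit passes 7%.

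**Step 5: can the cut-off be relaxed?** No. Allowing 2 recurrences in 35 gives a type I error of 19.2% at a true 12%.

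**Step 6: fewer evaluable patients.** With 30 evaluable, P(X ≤ 1) at 12% is 0.0216 + 0.0884 = 11.0%, above the planned 10%.

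**The case against.** The strongest defence is that 2.5% fits the plan's own ambition. Section XIII.A aims for less than 3%, and Section XI.B gives 7% as an upper bound, not a point expectation. Power is stated conditionally on 2.5% or less, and a 5-year 7% scaled to 2 years lands close to 2.5%. This stands as far as it goes: 2.5% does not contradict the stated expectation. But the plan does not offer that derivation. Even at the scaled rate power is 73.5%, and at the edge of the under-3% aim it is 71.7%.

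Several stronger readings are tempting, and the documents do not support them:

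- *The plan expects 7%, so a 71% failure rate is the result.* It expects below 7%, and the 71% applies only if 7% is the true 2-year rate.
- *Two or more recurrences will be declared inferior.* Section XIII.D speaks only of rejecting or not rejecting. Section XIV.A also reports cumulative incidence, and Section XI.D compares results with an institutional conventional-fractionation database.
- *The cited hypofractionation data refute 2.5%.* The 272-patient series, where "3-year overall survival was 72% and local control was 80"%, gave 25 Gy in 5 fractions rather than 35 Gy. The series at 35 Gy in 5 fractions reported 100% local control, though in only 12 patients. Neither settles the rate.
- *The trial is too small and must grow.* Reaching 80% power at a true 7% would take at least 155 patients (at most 13 recurrences; type I error 0.0996, power 0.802). A single-arm pilot need not do that; it should say plainly what 35 patients can show.

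**Conclusion.** The concern holds as a matter of disclosure and interpretation and should be fixed; it does not invalidate the design. The 12% limit and the rule of at most 1 recurrence are sound as a test of whether 2-year recurrence is below 12%, and at n = 35 the rule is stricter than stated (6.6% type I error against 8.97%). What fails is the power statement. It is wrong for 35 patients at the assumed rate (78.2%, not 81.0%). It is also silent about a regimen that matches the standard, where power lies between 28.7% and 73.5% depending on the standard's 2-year rate, which the documents do not give.

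These figures assume independent outcomes and all 35 patients evaluable at 2 years. The upper end of the range also assumes a constant hazard and that the 7% derives from the 5-year 93%, which the plan does not state.

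**What to change.** Keep 35 patients and the rule of at most 1 recurrence, and amend Section XIII as follows.

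1. Correct XIII.B to D to a type I error of 6.6%, an observed rate of 2.9% (1/35) and power of 78.2% at 2.5%. Delete the claim of at least 80% power at 2.5%, since 80% holds only at 2.36% or below. State power at 3% (71.7%), 5% (47.2%) and 7% (28.7%). Give the reason for 2.5%, and say how the three targets relate and whether 7% is a 2-year or a 5-year rate.
2. Name the positive conclusion *2-year local recurrence below 12%* instead of equivalence.
3. State that 2 to 4 recurrences of 35 is inconclusive and not evidence of inferiority, and that 5 or more puts the one-sided 90% lower limit above 7%. Recompute the limits, and recheck the rule's type I error, for the number actually evaluable at 2 years, because Sections X.D and X.E neither replace withdrawn patients nor continue their follow-up.

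The cost is protocol wording and a less favourable stated power. No patients, visits or procedures are added.
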